Sample 1 – Participants. To meet recruitment goals, we will aim to enroll 38 pregnant women per year (~3-4 women/month). Inclusion criteria: females 18-35 years old, in stable physical/mental health with confirmed pregnancy, self-reports smoking ≥ 5 cigarettes/day for the past year, has established prenatal care, single gestation, either 12-22 or 32-37 weeks gestation, English fluency, and able to provide informed consent. Exclusion criteria: use of psychotropic medications or illicit drugs with the exception of marijuana use ≤ 2 times per month and a willingness to abstain from marijuana during the testing period, current use of other types of tobacco or nicotine, or pregnancy complications (i.e. gestational diabetes, known congenital anomaly, fetal growth restriction, pregnancy hypertension and history of >2 miscarriages). Finally, participants will not be eligible to participate in the study at more than one time point (i.e. 12-22 and 32-37 weeks gestation) due to the potential ethical issues associated with administering nicotine nasal spray multiple times during pregnancy and/or unintended encouragement to continue smoking to be eligible to participate again.

Sample 1 - Timing of Testing Period. The testing period will occur during either 12-22 or 32-37 weeks gestation (participants complete one testing period only). These gestational weeks were selected to capitalize on the expected variability in sex hormones (e.g. 12-22 weeks gestation expected progesterone values are **19.5** to 89.4 ng/mL and 32-37 weeks gestation expected progesterone values are 48.4 to 200.0 ng/mL).²⁰ We will not be assessing the first trimester (due to the high risk for miscarriage and delay of initial prenatal care) nor late third trimester (due to the possibility of early delivery).

Sample 1 - Follow-up. After completing the testing period (described below) participants will receive smoking cessation behavioral counseling, self-help materials, advice for pharmacotherapy (and a prescription, if necessary) per the discretion of the study physician ([name], PI) and referrals to smoking cessation programs. Additional weekly phone counseling will be offered.

Sample 2 - Participants. To meet recruitment goals, we will aim to enroll 27 OC users per year (~3 women/month).

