Salivary Cortisol and mSSS ^{8*}			X			
Dependent Variables (Aim 2)						
Physiological Response (Blood Pressure, Pulse)					X	X
Subjective Response (SSS) ⁹					X	X
Behavioral Response (FT, WR, 2B, IMT, DMT) ¹⁰					X	X
Plasma Nicotine						X
Other Items						
Informed Consent	X					
Liver Function Tests ¹¹	X					
Demographics	X					
Medical History	X					
Smoking Behavior ¹²	X					
Adverse Events (including C-SSRS)	X	X		X	X	X
Expired Carbon Monoxide	X	X		X	X	X
Urinary Cotinine and 3-Hydroxycotinine		X		X		X

These items will be collected five times during the course of Day 5 only – at waking, 30 minutes later, two hours later, 8:00 pm and at bed time. ¹ Minnesota Nicotine Withdrawal Scale, Hughes & [name], 1998; ² Brief Questionnaire of Smoking Urgency, Tiffany & Drobes, 1991; ³ Modified Cigarette Evaluation Questionnaire, Cappelleri et al, 2007; ⁴ Positive and Negative Affect Schedule, Watson et al, 1988; ⁵ Cohen Perceived Stress Scale, Chaaya et al, 2010; ⁶ Center for Epidemiologic Study – Depression Inventory, Derogatis & Spencer, 1982; ⁷ Modified Subjective State Scale, [name], et al., 1998, [name] et al, 2003; ⁸ Lesiure Time Exposure Questionnaire, Godin & Shephard, 1983; ⁹ Subjective State Scale, [name], et al., 1998 and [name] et al, 2003; ¹⁰ Behavior tasks include Fingertapping, Hindmarch, 1980, Word Recall, Phillips & Fox, 1998, 2-Back, Meyers et al, 2008, Immediate Memory Task, Dougherty et al, 2002; ¹¹ Liver function tests of ALT and AST will be conducted in Sample 2 (OC only). ¹² Includes Fagerstrom Test of Nicotine Dependence (FTND), age of smoking initiation, number of past quit attempts, longest past quit attempt, motivation to quit smoking and TimeLine FollowBack (TLFB).

support for cessation. Based on observations in our current study, it is expected that up to 20% of women will want to maintain their smoking abstinence. If the participants want to return to smoking, they will be instructed to smoke at their 'regular rate' for the next three weeks and then attend an identical second testing period during the opposite testing phase (i.e. "low" or "high" dose).

Data Collection Procedures. All participants (Sample 1 and Sample 2) will complete identical testing procedures as described below and in **Table 2**.

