At the *follow-up clinic visit (Day 6)*, participants will return to the clinic. Upon arrival, participants will have their weight measured and provide urine (nicotine exposure and medication compliance via visual inspection of urine color which will change due to riboflavin medication filler) and blood (sex hormones) samples. Remaining blood and urine will be saved in the biorepository. Next, participants will complete self-reported items of smoking-related symptomatology and related factors (See Table 2 and Section E.5 for details) followed by measurement of blood pressure and heart rate. While participants are completing the questionnaires study staff may complete a NicAlert (Appendix C) to confirm self-reported smoking status (NicAlert level of ≥ 3 indicating a cotinine value of ≥ 100 ng/mL). Participants will then practice using the nicotine nasal spray but will be prompted to refrain from smoking for one hour prior to the visit to limit nicotine exposure. They will also practice smoking through the smoking topography machine and practice using the computer tasks and other measures used in the lab sessions (See Section E.5. for details). Finally, participants will be instructed to quit smoking by midnight (Appendix D). Upon the completion of this visit, the lab session will be confirmed and participants will be compensated for their time.

Figure 6. Nicotine Lab Sessions

The *smoking lab session*

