The *nicotine exposure lab session* will occur on *Day 8*. Participants will attend this four and a half-hour visit in the morning (beginning at 7am-10am depending on participant preference) to control for diurnal variation in outcome variables. While participants are completing the questionnaires study staff will download the information from the EDCs. Procedures will be identical to Day 7 except instead of subject smoking a cigarette, they will administer nicotine nasal spray and repeat the protocol twice. Nicotine nasal spray (Nicotrol, Pharmacia & Upjohn; Appendix A) is an FDA-approved use of nicotine delivery. One spray delivers 0.5 mg of nicotine; therefore, one dose (four sprays - two in each nostril) is approximately equivalent to the

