nicotine delivery from two cigarettes.⁴²⁻⁴⁴ The nasal spray is the only available delivery method that closely mimics the kinetics of smoking, is easy to administer, and delivers a consistent dose.⁴²⁻⁴³ While the nicotine nasal spray results in an adverse burning sensation, this sensation resolves on its own within minutes. In our current study we have completed over 400 nicotine nasal spray lab sessions and have never had to postpone data collection due to problem with the adverse effects of the nasal spray. We also chose the nicotine nasal spray because: (a) there are ethical and practical difficulties of instructing people to inhale measurable amounts of tobacco smoke from cigarettes, (b) it is difficult to control nicotine intake via smoke inhalation, (c) the spray isolates the effects of nicotine from that of the many other compounds found in tobacco smoke, (d) it has the fastest delivery system and best approximates the rise in nicotine concentrations as seen with cigarette smoking, and (e) it has been given a Pregnancy Category Risk of D – indicating that although nicotine has known adverse effects, the benefits of use may outweigh the risks. While there may be some initial concerns with administering nicotine to a pregnant woman, nicotine replacement products have been recommended for smoking cessation during pregnancy.⁴⁵ In a recent study by Oncken and colleagues,⁴⁶ 11 doses of nicotine nasal spray were administered over a six-hour period in a sample of pregnant smokers who abstained from smoking overnight. This study found that nicotine nasal spray reduced overall maternal nicotine exposure compared to active smoking. Compared to the 11 doses used in this study, our study will be using a single dose of nicotine nasal spray (less than 5% of the acceptable maximal dose and less than 10% of the dose used by Oncken and colleagues); therefore, there are limited ethical concerns with using nicotine nasal spray within our sample of pregnant smokers. Further this protocol was reviewed by a bioethicist at the University of Minnesota, [name], who felt there were no major ethical issues in administering this dose of nasal nicotine spray to pregnant women (see Section 2.14 for letter of support). In order to access plasma nicotine levels, a blood draw via an intravenous catheter will occur at baseline (-1 minute before the nasal spray) and at the expected maximum concentration (+5 minutes after the nasal spray; [name] et al, 2012). Blood collected at baseline will also be used to analyze sex hormones, more specifically progesterone and allopregnanalone. A total of 30cc of blood will be collected, 15 cc of blood will be analyzed for nicotine levels and hormone levels and 15 cc of blood will be added to the biorepository. Participants will also provide a urine sample to assess nicotine exposure and medication compliance via visual inspection of urine color which will change due to riboflavin medication filler. Remaining urine will be saved in the biorepository. Upon completion of the four and a half-hour lab session, any possible adverse events will be assessed for all participants. Finally, all participants will be compensated for their time and will be offered brief smoking cessation counseling and self help materials for smoking cessation.

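### The Day 8 instruction can be read as two or three nicotine spray doses, while the pregnancy safety argument holds only for one

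*Combined protocol and SAP*

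**What the plan says.** All four statements below are in the combined protocol and SAP, under Data Collection Procedures unless noted.

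- **Operative instruction.** The paragraph on the nicotine exposure lab session makes Day 8 the same as Day 7, except that instead of smoking a cigarette "they will administer nicotine nasal spray and repeat the protocol twice". The opening of the section applies this to both samples: "All participants (Sample 1 and Sample 2) will complete identical testing procedures as described below".
- **Dose definition.** "One spray delivers 0.5 mg of nicotine; therefore, one dose (four sprays - two in each nostril"), described as about equal to the "nicotine delivery from two cigarettes".
- **Safety argument.** The same paragraph contrasts 11 spray doses over six hours in an earlier study of pregnant smokers with this study's use of "a single dose of nicotine nasal spray (less than 5% of the acceptable maximal dose and less than 10% of the dose" in that study. It concludes that ethical concerns are limited and cites a bioethicist's opinion on this dose.
- **Day 6 practice.** At the follow-up clinic visit participants "practice using the nicotine nasal spray but will be prompted to refrain from smoking for one hour prior to the visit to limit nicotine exposure". No amount is given.

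Sample 1 – Participants bars a woman from taking part at both gestational windows, partly "due to the potential ethical issues associated with administering nicotine nasal spray multiple times during pregnancy".

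**The concern.** The instruction names the spray and then orders a repeat, so a staff member could reasonably repeat the spray as well. Depending on whether the word twice means two runs in all or two further runs, that gives two or three doses. The safety text counts one. Nothing in the visible text says which part of the Day 8 procedure is repeated, and pregnant participants are not exempted.

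At stake is the nicotine given to pregnant women in Sample 1. If the spray were repeated, they would receive two or three times the dose on which the ethical argument and the cited opinion rest, and the stated 10% bound would no longer hold. The bar on a second testing period suggests that the authors regard repeated spray in pregnancy as material. That support is indirect, because the bar concerns two gestational windows and not repeats within one session.

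**Working it through.** **Inputs.** 0.5 mg per spray and four sprays per dose (dose definition); one dose is about two cigarettes (same place); 11 doses in the comparison study, with this study's share put below 10% (safety argument); entry criterion "self-reports smoking ≥ 5 cigarettes/day for the past year" (Sample 1 – Participants).

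**Step 1: reproduce the plan's figure.** Share by dose count = k/11, where k is the number of Day 8 doses. For k = 1, 1/11 = 9.1%. This agrees with the stated bound.

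**Step 2: apply the other readings of the instruction.** Equal-size doses are assumed in the share column.

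| Day 8 doses | Share of 11 doses | Nicotine | Approximate cigarettes |
|---|---|---|---|
| 1 | 1/11 = 9.1% | 4 × 0.5 = 2 mg | 2 |
| 2 | 2/11 = 18.2% | 4 mg | 4 |
| 3 | 3/11 = 27.3% | 6 mg | 6 |

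The last two columns do not depend on the comparison study. The entry minimum of 5 cigarettes a day gives them scale.

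**Step 3: what the 10% bound needs.** By count, 10% of 11 is 1.1 doses, so one dose meets the bound and two do not. The documents do not give the comparison study's dose in mg. If the comparison is made in mg, the bound requires a comparator dose above 2/(11 × 0.10) = 1.82 mg for one Day 8 dose, 4/1.1 = 3.64 mg for two, and 6/1.1 = 5.45 mg for three. The other figure, below 5% of the maximal dose, cannot be checked because the maximum is not stated. Taken at face value, it would guarantee only below 10% for two doses and below 15% for three.

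**Step 4: which reading does the rest of the text fit?**

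- *One dose.* The safety argument gives the only explicit count, which is one. The Day 8 paragraph and the plasma nicotine item under Study Measures schedule one blood draw at −1 minute and one at +5 minutes, 30 cc in total. Day 7, with one cigarette, also totals 30 cc. Statistical Analysis defines a single pre-spray baseline for each measure and analyses heart rate five minutes after the spray. No second baseline, draw or second-dose outcome appears.
- *Repeated spray.* The wording of the instruction. Day 8 also runs four and a half hours against three on Day 7.
- *Visit length does not decide it.* The tasks with stated times total 2 + 1.5 + 4 + 6 + 6 + 6 = 25.5 minutes. Three full batteries take 76.5 minutes, less than the extra 90 minutes, so repeated measurements after one spray could fill the time.
- *Table 3* calls Day 8 a three-hour session, against four and a half hours in the Overview and the Day 8 paragraph. This seems to fit one dose, but the table also lists hormones on Days 0 and 7 where Study Measures lists Days 0, 6 and 8. It may be out of date, so little weight is placed on it.

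**The case against.** The strongest reply is that the plan already says one dose and that the instruction refers to measurements. The Overview describes a single nicotine challenge followed by a timed series of responses. The Subjective State Scale is rated over a look-back that depends on when it was last completed, so it is evidently given several times in a session. Statistical Analysis plans repeated-measures models over time points after the spray. On this reading the protocol that is repeated is the test battery, and Figure 6 may show as much. The plan also reports that the 11-dose study found lower overall maternal nicotine exposure with the spray than with active smoking. Two or three doses would still be well below 11 by count, so the ethical argument would not clearly fail.

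Most of this stands. One dose is the better-supported reading, and it is the reason for making it the default in the fix. What the reply does not do is remove the sentence that staff would follow, which can be read the other way.

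A reader might go further and infer that pregnant women will receive two or three doses, that the 10% figure was miscalculated, that the exposure is unsafe, or that the ethics opinion was exceeded. The documents support none of these. The dose count is ambiguous and leans towards one, the division is right, no harm is shown, and the bioethicist's letter is not among the documents.

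**Conclusion.** The point holds as an internal inconsistency in dosing text. The Day 8 instruction admits one, two or three spray doses on the visible wording, and the safety argument is true as written only for one. The difference is 9.1% against 18.2% or 27.3% of the comparison study by dose count, or 2 mg against 4 or 6 mg in one visit. The percentages are illustrative: they rest on equal-size doses and on the spray being part of what is repeated, which the sampling schedule, baseline and endpoint do not suggest.

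The Day 6 practice is a separate, smaller gap. Its amount is unstated, and the instruction to limit nicotine beforehand suggests, without saying, that the practice spray contains nicotine. It adds nothing to the Day 8 figures above.

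Confidence is medium, because Figure 6 may settle the count. The text should be corrected in any case: it governs nicotine given to pregnant women, and the correction is a few sentences.

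**What to change.** 1. In the Day 8 paragraph, replace the repeat clause with a statement that the spray is given once (four sprays, 2 mg), at least in Sample 1, and that only the measurement battery is repeated. The safety argument's Day 8 dose count and its below-10% comparison by count then stand.
2. Only if repeat dosing is truly intended: correct the single-dose statement and both percentages to the total Day 8 dose, give the comparator dose and the maximum used as denominators, and confirm that the ethics review covered that total.
3. In the Day 6 paragraph, state the practice amount in sprays or mg, or make practice nicotine-free.
4. Change Table 3's three-hour Day 8 session to the four and a half hours given in the Overview and the Day 8 paragraph.

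The cost is wording in the Day 6 and Day 8 paragraphs and Table 3. Ethics confirmation is needed only under item 2. No new data, visits or participants are required.

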will occur on *Day 7*. At this visit, participants will smoke their first morning cigarette (i.e. they will be instructed to not smoke on Day 7 until instructed to do so by study staff). Participants will attend a three hour visit beginning as close to their usual first morning cigarette as possible (starting at approximately 7am-10am, per participant preference). Puff topography, a precise measure of smoking behavior,^{67,68,69} will be used to examine whether prolonged use of progesterone affects topography measures that may indicate smoking compensation.⁷⁰ Puff topography will be assessed using a handheld topography device (type pending) that provides a valid measurement of puff number, puff volume, inter-puff interval and other indices.⁶⁶ Carbon monoxide readings will be collected before and 2-5minutes after puff topography.³⁶ Prior to the initiation of the lab session, participants will have their weight, blood pressure, and heart rate measured, and they will complete subjective measures to assess their self-reported level of smoking-related symptomatology and related factors after overnight abstinence (See Table 2 and Section E.3.5 for details). Once the smoking lab session begins, participants will be instructed to turn off their cell phones and will not be allowed to consume caffeinated beverages or any food items. Measurements of smoking response will start 40 minutes prior to the participant smokes her cigarette and will be administered in a fixed order (**Figure 6**). Response to smoking will be quantified via seven performance domains known to be associated with nicotine response:⁴¹ (1) physiological (blood pressure, heart rate), (2) subjective (Subjective State Scale); (3) motor speed (Finger Tapping) (4) episodic memory (Word Recall); (5) working memory (2-Back); (6) attention/impulsivity (Immediate Memory Task), and (7) delayed memory (Delayed Memory Task). (See Section E.5. for more details.) In order to access plasma nicotine levels, a blood draw via an intravenous catheter will occur at baseline (-1 minute before smoking a cigarette) and +2 minutes after the last puff of the cigarette. A total of 30cc of blood will be collected. 15 cc of blood will be analyzed for nicotine levels and hormone levels and 15 cc of blood will be added to the biorepository.

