
Study Participant Compensation. All participants will receive \$10 at the screening visit, \$20 at the baseline visit, \$10 at the interim visit, \$20 for Follow-up Visit on Day 6, \$20 for Smoking Lab Session on Day 7 and \$50 for the Nicotine Exposure Lab Session on Day 8. They will also receive \$5 for each EMA completed with a bonus of \$20 for not missing any EMAs, and \$1 for each cortisol salivary sample collected with a bonus of \$20 for not missing any of the five samples. A bonus of \$100 will be given for completing all study procedures and \$120 for returning the study supplied EDCD. Thus, all participants in Sample 1 will be compensated a total of \$510 for completing the study. The participants in Sample 2 will have the potential to earn \$ 900 by completing the testing week twice.

Study Measures. The independent measures will be the serum levels of progesterone (Prog), allopregnanolone (Allo), and the estradiol/progesterone (E2/P) ratio. Measurement of hormones will be done by collecting a blood sample on the baseline, follow-up, and nicotine nasal spray lab visits (Day 0, 6, and 8). We have opted to collect blood samples three times to allow for average hormone levels during the testing period to be obtained. Blood (20 cc) will be drawn then centrifuged. The serum stored at -20°C in sealed storage tubes to prevent evaporation. Approximately two mL of serum will be analyzed by the Fairview University Medical Laboratories for progesterone and estradiol samples using chemiluminescence. The expected values for these tests are displayed in Figure 6. Approximately two mL of serum will be sent to [name] lab at the University of California, San Diego (see Section 2.14 for letter of support) for Allo level measurement using radioimmunoassay techniques previously described.⁴⁷ The remaining serum (approximately two to four mL) will be stored as back-up.

For Aim 1, the outcome is the level of smoking-related symptomatology during ad libitum smoking. Items 1-7 below will be measured an average of three times a day for seven days via the EMAs. We selected the seven day testing period given that the hormones fluctuate fairly rapidly; thus, measuring symptomatology for longer than seven days would make the association between sex hormones and symptomatology more difficult to assess. For each item, participants will be instructed to rate their symptoms since the last assessment. The following nine dependent measures will be used (Appendix B):

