- (1) Minnesota Nicotine Withdrawal Scale (MNWS): Participants rate their nicotine withdrawal symptoms on eight-items on a scale of '0' (not present) to '4' (severe) resulting in summary scores overall withdrawal and craving.²⁵
- (2) Questionnaire on Smoking Urges-Brief (QSU-Brief): This ten-item version of the original form (QSU) was developed by Tiffany and Drobes²⁶ and has an excellent level of reliability ($\alpha = .97$). Two factors are obtained: 'Factor 1' is a measure of primary intention and desire to smoke and 'Factor 2' is a desire to smoke in anticipation of relief from negative affect.
- (3) Modified Cigarette Evaluation Questionnaire (mCEQ): This 12-item questionnaire uses a seven-point Likert-type scale to assess the reinforcing effects of smoking resulting in five domains including smoking satisfaction, psychological reward, aversion, enjoyment of respiratory tract sensations and craving reduction.²⁷
- (4) Positive and Negative Affect Scale (PANAS): Participants rate 20 words associated with positive or negative affect using a five-point Likert-type scale. This scale has been shown to have high internal consistency.⁴⁸
- (5) Cohen Perceived Stress Scale (PSS): This ten-item questionnaire has been validated in a variety of populations including pregnant and postpartum women. It uses five-items to assess ten questions resulting in two factors negative feelings and inability to handle stress. It has high internal reliability ($\alpha = 0.75$).⁴⁹
- (6) Center for Epidemiologic Studies – Depression (CES-D): This form contains ten-items to assess symptoms typically associated with depression. The items are ranked using a four-point Likert-type scale. It has high levels of sensitivity and specificity.⁵⁰⁻⁵¹ We have opted to use this item rather pregnancy-specific item to ensure that all participants had comparable data.
- (7) Leisure Time Exercise Questionnaire (LTEQ): This questionnaire has four-items to assess strenuous, moderate and mild exercise completed during leisure time and has high reliability ($r=0.83, 0.85$).⁵²
- (8) Monitoring Subjective State Scale (mSSS, Day 5 only): This form is identical to the Subjective State Scale (SSS)⁵³⁻⁵⁴ except it also includes variables to assess possible confounders such as coffee consumption. Participants will be asked to mark each rating scale at the point that best describes how they felt over the past 30 minutes.

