- (9) Salivary Cortisol (Day 5 only): Five saliva samples over the course of the day given that cortisol, a physiological measure of stress released by the hypothalamic-pituitary adrenal axis (HPAA), has a clear diurnal variation. Its peak activity occurs about 8:00 am in the normal sleeper, followed by steady decline until noon. The lowest activity occurs around 8:00 pm. The frequent sampling in the morning will be used to assess free cortisol responses to awakening. Awakening cortisol increase is considered a promising marker of adrenocortical functional status.⁵⁵⁻⁵⁷

For Aim 2, the outcomes will be assessed following overnight abstinence: (1) the change in smoking-related symptomatology (items 1-6 above), and (2) response to nicotine (described below). We have a nearly identical timed series to assess nicotine response with success in our ongoing study. All items will be self-administered per direction of study staff via a computer program (REDCap; <http://project-redcap.org/>) to improve the quality of data (by avoid missing data, illegible data, etc) and limit amount of time spent on data entry and cleaning. The following seven *dependent measures* were selected to assess seven domains of nicotine response:⁴¹

- (1) Physiological Measures: Blood pressure (BP) and heart rate (HR) will be measured using a Dinamap S X/P. This device is an automated device that will read BP and HR simultaneously by placing a blood pressures cuff above the antecubital fossa region of the arm.
- (2) Subjective Response: The Subjective State Scale (SSS) questionnaire is comprised of 24-items to assess positive affect, distress and nicotine withdrawal symptoms.⁵³⁻⁵⁴ Participants will rank each item based on how they felt over the past 5-30 minutes (depending on time of last completion) using a seven-point scale ranging from 'not at all' to 'very strong.' This form takes approximately two minutes.
- (3) Motor Speed: During the Finger Tapping (FT) task,⁵⁸ participants are instructed to use the index finger on the dominant hand to tap a key on a computer as quickly as possible for 30 seconds. This task takes about 1.5 minutes.

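### The mCEQ rates cigarettes that were smoked, so its change to Day 8 is not a response to abstinence; Day 7 gives it before the lab cigarette, and the EMA sets no smoking condition

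*Combined protocol and SAP*

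**What the plan says.** Study Measures, item (3), describes the mCEQ as a 12-item, seven-point form used to "assess the reinforcing effects of smoking resulting in five domains including smoking satisfaction, psychological reward, aversion, enjoyment of respiratory tract sensations" and craving reduction.

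- **Aim 1 (EMA).** "Items 1-7 below will be measured an average of three times a day for seven days via the EMAs", so the mCEQ is included. The recall instruction reads "For each item, participants will be instructed to rate their symptoms since the last assessment".
- **Aim 2.** "For Aim 2, the outcomes will be assessed following overnight abstinence". The first outcome is "the change in smoking-related symptomatology (items 1-6 above", with no exception for item 3. Table 2 ticks the mCEQ at every time point, including Days 7 and 8.
- **Day 7 (smoking lab session).** Women stop smoking by midnight on Day 6. Before the session starts, "they will complete subjective measures to assess their self-reported level of smoking-related symptomatology and related factors after overnight abstinence". The lab cigarette comes later.
- **Day 8 (nicotine exposure lab session).** The Overview requires at least 13 hours of abstinence. Procedures repeat Day 7 with nasal spray in place of the cigarette.
- **Analysis.** The Statistical Analysis section names craving (primary), urges, stress and mood. It does not name the mCEQ. Similar analyses are promised for secondary outcomes.

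The text supplied has no skip rule, no not-applicable option and no scoring rule for an interval without a cigarette.

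**The concern.** Withdrawal, urge, affect, stress and depression scales can be answered whether or not a woman has smoked. The mCEQ cannot: each of its domains needs a cigarette to rate. Asked after overnight abstinence, it will be left blank, scored low because nothing was smoked, or answered from memory of earlier cigarettes. A change from ad libitum smoking to abstinence then mixes reinforcement with the mere absence of a cigarette.

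The EMA carries a milder form of the problem. The share of ratings with no cigarette behind them rises as a woman smokes less. If smoking rate differs by hormone level or dose, the mean mCEQ can shift with no change in reinforcement, and the shift could be read as a hormone effect. The team's preliminary Study #3 found its satisfaction and enjoyment signals on this scale, so it is likely to be analysed.

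**Working it through.** **1. Aim 2, Day 8.** No arithmetic is needed to establish the problem. Item (3) defines the score by effects of smoking; the Overview puts at least 13 hours without smoking before the session; the Day 8 text substitutes nasal spray for the cigarette. So the form refers either to no cigarette or to one smoked before abstinence began. Neither measures what abstinence did.

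**2. Day 7.** The forms come before the lab cigarette. They may still refer to the previous evening, because prompts end by 11PM and smoking may continue to midnight. Take the EMA recall window, and assume C cigarettes spread uniformly over 7AM-midnight (17 h) and P fully random prompts over 7AM-11PM (16 h). The chance of no cigarette between the last Day 6 prompt and midnight is (16/17)^C × P/(C+P).

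- C=5, P=3: 0.739 × 0.375 = 0.277, so 72% of windows contain a cigarette.
- C=5, P=4: 0.739 × 0.444 = 0.328, so 67%.
- C=20, P=3: 0.297 × 0.130 = 0.039, so 96%.

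With one prompt per equal time block and C=5, the figures are 66% (P=3) and about 60% (P=4). Day 7 scores are therefore ambiguous rather than empty.

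For Day 8, 13 hours before a 7AM-10AM start puts the last cigarette at 6PM-9PM. Simulation under the same kind of assumptions gives a cigarette in the window in 0% to about 56% of cases.

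**3. EMA.** Inputs from the documents: at least 5 cigarettes/day at entry (both samples), random prompts over 16 hours, average 3 and at most 4 a day, seven days. Assumed: cigarettes uniform over the same 16 hours, rates above 5/day, and the prompt scheme.

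For fully random prompts, the chance that the gap between two same-day prompts has no cigarette is q = P/(C+P). The first prompt of Days 2-7 spans two part-gaps (q²); the first prompt on the first day spans one (q). The share is {6 × [(P−1)q + q²]/P + q}/7.

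- C=5, P=3: q = 0.375; [2(0.375) + 0.1406]/3 = 0.297; (6 × 0.297 + 0.375)/7 = 0.308.
- C=5, P=4: q = 0.444; [3(0.444) + 0.198]/4 = 0.383; (6 × 0.383 + 0.444)/7 = 0.391.

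Simulation gives 0.306 and 0.390. All simulated shares of prompts with no cigarette since the previous one:

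| Cigarettes/day | Random, 3 prompts | Random, 4 prompts | One per block, 3 prompts | One per block, 4 prompts |
|---|---|---|---|---|
| 5 | 31% | 39% | 21% | 30% |
| 10 | 18% | 24% | 8% | 12% |
| 20 | 10% | 14% | 3% | 4% |

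**4. What the smoking-rate dependence could do.** As an illustration, suppose intervals with smoking average 4 on the seven-point scale and empty intervals are scored 1 (both assumed). Moving from 10 to 5 cigarettes/day at 3 prompts lowers the mean by 3 × (0.306 − 0.179) = 0.38 points with random prompts, or 3 × (0.207 − 0.082) = 0.38 with blocks, though reinforcement is unchanged.

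**The case against.** Several counter-arguments stand and limit the point.

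- **Minor role.** The Statistical Analysis section does not name the mCEQ, and the Sample 2 post-abstinence analysis lists craving, urges and stress. The scale enters only through the general sentence on secondary outcomes. No primary hypothesis or power figure rests on it.
- **Recall window.** The since-last-assessment instruction appears only in the Aim 1 EMA paragraph. A reader might infer that every post-abstinence mCEQ score is empty. The documents do not support that: the window is not stated for the clinic forms, and Day 7 scores can refer to smoking up to midnight on Day 6.
- **Pilot evidence.** A reader might cite Studies #2 and #3 together as reinforcement findings. Study #2 reported craving; only Study #3 reported satisfaction and enjoyment.
- **Day 7.** EMA prompts continue through Day 7, so a later rating may include the lab cigarette, mixed with any smoked afterwards. What is missing is a rating straight after it.
- **Adjustment.** Sample 1 models are refitted with cigarettes/day, and a smoking-reduction indicator with its interaction is planned. This helps partly, but does not remove empty intervals. The Sample 2 model has only dose, period and sequence.
- **Unseen forms.** The instruments are in Appendix B, which is not in the text supplied, so a skip rule cannot be excluded. The EMA content list under Data Collection Procedures does not name reinforcement, although Study Measures includes item 3.

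None of this rescues the Day 8 change score.

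**Conclusion.** The point holds for Aim 2 and needs no assumption beyond compliance: a mCEQ change to Day 8 cannot be read as a response to abstinence. On Day 7 the score is ambiguous, and the one observed cigarette has no scheduled rating straight after it. Table 3 also labels Day 7 symptomatology as ad libitum while the Day 7 procedure places it after overnight abstinence; these must be reconciled.

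For the EMA the size depends on assumed spacing and smoking rate: material near the entry floor, small for heavy smokers. A reader might infer that a spurious hormone effect will follow. The documents do not show that. They give no consumption distribution, and a link between hormone level or dose and smoking rate is a possibility, not a stated fact. The consequence is limited to interpretation of one secondary scale.

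**What to change.** 1. Remove item 3 from the Aim 2 abstinence-change outcomes, leaving items 1, 2 and 4-6.
2. On Day 7, give the mCEQ once straight after the lab cigarette and analyse it as a secondary reinforcement outcome against hormone level (Sample 1) or dose (Sample 2).
3. In the EMA, use the smoking report already collected to show or analyse the mCEQ only for intervals with smoking. Report the number of such intervals by hormone level or dose. If Appendix B already has a skip rule, the protocol need only state it.

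The cost is one edited line, one relocated 12-item form and one skip or analysis rule; the sample size is untouched. There are two real downsides. Fewer EMA ratings per woman remain, and their average is conditional on smoking, a behaviour that hormones may themselves affect, so it must be interpreted that way. The Day 7 score is a single rating after smoking through a topography device, and may not represent usual smoking.
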